#### 8.2 Secondary Objectives

The secondary objectives are to determine whether the liberal strategy is superior to a restrictive strategy in terms of:

- 1. Incidence of each individual component of the primary outcome: all-cause mortality, myocardial infarction, new onset renal failure requiring dialysis, and new focal neurological deficit (stroke) within 6 months
- 2. Composite and individual all-cause mortality, myocardial infarction, new onset renal failure requiring dialysis, and new focal neurological deficit (stroke) with index hospitalisation or after 28 days postoperatively, whichever comes first
- 3. Length of stay in the Intensive Care Unit (ICU) and hospital (index hospitalisation)
- 4. Prolonged low output state defined as the need for two or more inotropes for 24 hours or more, intra-aortic balloon pump or ventricular assist device postoperatively (index hospitalisation)
- 5. Duration of mechanical ventilation (index hospitalisation)
- 6. Infection: defined as septic shock with positive blood cultures; pneumonia defined as autopsy diagnosis or roentgenographic infiltrate and at least two out of three of the following criteria: fever, leukocytosis, and positive sputum culture; and/or deep sternal or leg wound infection requiring intravenous antibiotics and/or surgical debridement (index hospitalisation)

Page **21** of **55** 

IRAS ID: 325425

- 7. Acute kidney injury (AKI), defined by the Kidney Disease Improving Global Outcomes (KDIGO) clinical practice guideline  $^{46}$  a 50% increase in serum creatinine within 1 week or a 26.5  $\mu$ mol/L increase within 48 hours (index hospitalisation)
- 8. Delirium, based on one of the following criteria: Confusion Assessment Method (CAM) or CAM-ICU (even on 1 occasion), or Intensive Care Delirium Screening Checklist (ICDSC) > 3, or 3D-CAM, or 4AT ≥4, or more than one dose of haloperidol or similar antipsychotic drug, or documented delirium by neurologist or neurosurgeon or psychiatrist consultation (index hospitalisation)
- 9. Gut infarction confirmed by imaging (e.g. angiography), autopsy, or through surgical means (index hospitalisation)
- 10. Hospital visits (hospitalisation and/or emergency visits and coronary revascularisation at 6 months)
- 11. The proportion of patients transfused and the number of blood products utilised (RBCs, plasma, platelets) (index hospitalisation)

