#### 9.2 Exclusion Criteria

- 1. Patients who refuse participation
- 2. Patients who are unable to receive or who refuse blood products
- 3. Patients who are involved in a preoperative autologous pre-donation program
- 4. Patients who are having a heart transplant or having surgery solely for an insertion of a ventricular assist device
- 5. Pregnancy or lactation (a negative pregnancy test must be obtained prior to randomisation for women of childbearing potential)

Page 22 of 55

IRAS ID: 325425

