#### 10.4 Blinding

The trial allocations cannot feasibly be blinded, and therefore this is designed as an open label trial. Adjudication of postoperative myocardial infarction, cerebrovascular accident, infectious and renal outcomes will be blinded, nonetheless.

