#### 14.12 Clinical Events

14.12.1 Clinical events from the start of surgery until hospital discharge or postoperative day 28, whichever comes first

The following clinical events will be assessed through review of the patient medical records/chart, and reported in the eCRF from the start of the index cardiac surgery until discharge or postoperative day 28, whichever comes first. All definitions are standard definitions.

- All-cause mortality
- Myocardial infarction which will be defined in accordance with the 4th Universal Definition of Myocardial Infarction
  - a) Early perioperative MI (intraoperatively or within 48 hours after surgery): Detection of cardiac troponin (preferred) or CK-MB values more than 10 times the 99th percentile of the upper limit from a normal baseline\* (i.e. the 99th percentile or less of the upper limit of normal) during the first 48 hours following surgery, and at least one of the following:
    - development of new pathological Q waves on the ECG
    - imaging evidence of new loss of viable myocardium or new regional wall motion abnormality
    - identification of a coronary dissection, new intracoronary thrombus of the new graft or native coronary artery(ies) by angiography or autopsy
    - Although a new left bundle branch block is not part of the 4th Universal Definition, we will
      include the collection of left bundle branch block to permit comparison to data collected
      in TRICS III that complied with the 3rd Universal Definition, which included left bundle
      branch block

\*or, if preoperative cardiac enzymes are elevated, the postoperative enzymes are increased by more than 10 times the upper limit of normal (ULN) from the baseline value (i.e. greater than baseline plus 10 x the ULN).

- b) Late perioperative MI (more than 48 hours after surgery): Detection of a rise and/or fall of cardiac troponin (preferred) or CK-MB values, with at least one value above the upper limit of normal, and with at least one of the following:
  - symptoms of ischemia, as long as the symptoms/signs are not explained by another proven clinical condition (pulmonary embolism, myocarditis, etc.)
  - new, or presumed new, significant ST-T wave changes or new left bundle branch block
  - development of new Q waves on the ECG
  - imaging evidence of new loss of viable myocardium or new regional wall motion abnormality

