  - identification of a new intracoronary thrombus of the new graft or native coronary artery(ies) by angiography or autopsy

Percutaneous coronary intervention (PCI) related MI is included in the late MI group, and is arbitrarily defined by elevation of troponin values more than 5 times the 99th percentile of the upper limit from a normal baseline, or a rise of troponin values more than 20% if the baseline values are elevated and are stable or falling. In addition, either (i) symptoms suggestive of myocardial ischemia, or (ii) new ischemic ECG changes, or (iii) angiographic findings consistent with a procedural complication or (iv) imaging demonstration of new loss of viable myocardium or new regional wall motion abnormality are required.

New onset renal failure requiring dialysis (excluding dialysis during CPB)

Page **32** of **55** 

IRAS ID: 325425

- New focal neurological deficit (stroke) lasting more than 24 hours confirmed by clinical assessment and brain imaging
- Infection: infection will be defined as septic shock with positive blood cultures; pneumonia defined as autopsy diagnosis or roentgenographic infiltrate and at least two of the following three criteria: fever, leukocytosis, and positive sputum culture; and/or deep sternal or leg wound infection requiring intravenous antibiotics and/or surgical debridement44
- Acute kidney injury: defined by the Kidney Disease Improving Global Outcomes (KDIGO) clinical practice guideline46 a 50% increase in serum creatinine within 1 week or a 26.5 μmol/L increase within 48 hours
- Delirium: based on one of the following criteria: CAM/CAM-ICU (even on 1 occasion), or ICDSC
   > 3, or 3D-CAM, or 4AT ≥4, or more than one dose of haloperidol or similar antipsychotic drug, or documented delirium by neurologist or neurosurgeon or psychiatrist consultation
- **Gut infarction:** confirmed by imaging (e.g. angiography), autopsy, or through surgical means
- **Seizures:** defined as generalised or focal tonic-clonic movements consistent with seizure; or EEG demonstrating epileptiform discharges; or diagnosis of seizures by neurologist or neurosurgeon consultation
- **Encephalopathy:** defined as unexpected delayed awakening or severely altered mental status (unconscious despite no sedative medication for more than 5 days), or encephalopathy documented by neurologist or neurosurgeon or psychiatrist consultation

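### Delirium and prolonged low output state can be scored from a drug or device already in use before surgery, because neither definition requires it to be new

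*Protocol*

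**What the plan says.** **Delirium** (Protocol sections 4, 8.2 item 8, 14.12.1, 15.2 item 7 and 19.5 item 8) is met by any one criterion in a list of screening tools, drug use and specialist documentation. The drug criterion is "more than one dose of haloperidol or similar antipsychotic drug". It stands alone: no new start, no indication and no finding on mental state is asked for. Delirium is among the events taken from chart review and "reported in the eCRF from the start of the index cardiac surgery until discharge or postoperative day 28, whichever comes first".

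**Prolonged low output state** (sections 4, 8.2 item 4, 15.2 item 3 and 19.5 item 3; it is not listed in 14.12.1) is the "need for two or more inotropes for 24 hours or more, intra-aortic balloon pump or ventricular assist device postoperatively". Nothing is said on when or why the device was placed.

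**Eligibility** (section 9.2) does not bar patients on antipsychotics or with a preoperative balloon pump. For assist devices, apart from heart transplantation, it removes only patients "having surgery solely for an insertion of a ventricular assist device".

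**Adjudication.** Section 10.4 states: "Adjudication of postoperative myocardial infarction, cerebrovascular accident, infectious and renal outcomes will be blinded". Section 17.6 and section 19.5 item 16 speak more broadly of clinical outcomes or events going to the adjudication committee, under a manual that is not shown.

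**The concern.** The protocol deals with baseline states elsewhere. In section 14.12.1, renal failure must be of new onset, the neurological deficit must be new, and the myocardial infarction rule has its own threshold for patients whose enzymes were raised before surgery. The drug criterion for delirium and the device criterion for low output state have no equivalent.

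Three kinds of patient meet the wording for reasons settled before surgery:

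- a patient on a regular antipsychotic who receives two home doses after surgery with a clear mind;
- a patient who arrives with a balloon pump that is still in place after surgery;
- a patient whose assist device was planned together with another procedure, and who is therefore not excluded by the rule on surgery done only for a device.

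Their event status cannot depend on the transfusion strategy. Counting them adds events that carry no information on treatment, so the relative effects on these two outcomes look weaker than they are.

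**Working it through.** **1. The plan's own figure.** No rate or power is stated for delirium or low output state. The only design figure is for the primary composite in section 16.1: 20% versus 14%, two-sided 0.05, 85% power, 1.5% loss, 1,440 patients. The pooled-variance formula is

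n per arm = [z(α/2)·√(2·p̄·(1−p̄)) + z(β)·√(p1(1−p1) + p2(1−p2))]² / (p1−p2)²

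= [1.96·√(2·0.17·0.83) + 1.036·√(0.16 + 0.1204)]² / 0.06² ≈ 703.

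Dividing by 0.985 gives 714 per arm, 1,428 in total. With the final critical value of 1.98 from section 16.6, it is 712 per arm, or 1,446 after loss. The stated 1,440 is reproduced within rounding of method, and neither endpoint discussed here enters it.

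**2. Model for the dilution.** Let p be the true event rate in an arm, and x the share of patients without a true event who are counted because of a preoperative drug or device. If x is the same in both arms:

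- observed rate = p + (1−p)·x
- observed risk difference = (1−x) × true risk difference

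The second line shows why the risk difference is almost untouched.

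**3. Numbers.** The documents give neither x nor p for these outcomes. The values below are assumptions, with a true risk ratio of 0.70.

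| True restrictive / liberal | x | Observed restrictive / liberal | Risk ratio | Odds ratio (true → observed) | Risk difference, points (true → observed) |
|---|---|---|---|---|---|
| 12% / 8.4% | 1% | 12.88% / 9.32% | 0.723 | 0.672 → 0.695 | 3.60 → 3.56 |
| 12% / 8.4% | 3% | 14.64% / 11.15% | 0.761 | 0.672 → 0.732 | 3.60 → 3.49 |
| 8% / 5.6% | 1% | 8.92% / 6.54% | 0.734 | 0.682 → 0.715 | 2.40 → 2.38 |
| 8% / 5.6% | 3% | 10.76% / 8.43% | 0.784 | 0.682 → 0.764 | 2.40 → 2.33 |

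Example, second row: 0.12 + 0.88 × 0.03 = 0.1464, and 0.084 + 0.916 × 0.03 = 0.1115; the ratio is 0.761. The restrictive-arm rate is inflated by 7 to 22% at a true 12%, and by 12 to 35% at a true 8%.

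**4. Wider range and power.** With a true restrictive-arm rate of 10% and 720 × 0.985 ≈ 709 evaluable patients per arm:

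| x | Risk ratio | Power (0.53 without dilution) |
|---|---|---|
| 0.5% | 0.714 | 0.50 |
| 1% | 0.728 | 0.48 |
| 2% | 0.751 | 0.44 |
| 5% | 0.803 | 0.36 |

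Over the same x, the risk ratio runs from 0.727 to 0.854 at a 5% rate and from 0.707 to 0.763 at a 20% rate. The rarer the true event, the stronger the dilution.

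**The case against.** **These are secondary outcomes and the dilution favours neither arm.** This stands. Section 16.5 reports risk differences alongside odds ratios, and the risk difference shrinks only by the factor (1−x). Every size above rests on assumed prevalences.

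**Adjudication may remove such cases.** A reader might infer from the list in section 10.4 that nothing stated reviews these two outcomes. Sections 17.6 and 19.5 item 16 do provide a broader review, so that inference goes too far. But an adjudicator who applies the written definitions would confirm the cases, since they meet them literally. Whether the unseen manual adds a newness rule cannot be told.

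**A persisting pump is real low output.** The definition speaks of need. A patient who still needs a preoperative pump after surgery arguably has the condition, so counting that patient is partly defensible. The argument is weaker for an assist device that was planned in advance.

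**Acute kidney injury might seem to share the flaw.** A reader might infer that patients on chronic dialysis count automatically. The text does not support this: the rule asks for "a 50% increase in serum creatinine within 1 week" or a smaller absolute rise within 48 hours. That is a change, and dialysis is not a criterion. What remains is evaluability: such patients are not excluded, and a rise between sessions could cross the threshold. The separate renal plan promised in section 16.5 and the blinded renal adjudication in section 10.4 may already settle it.

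**Open-label prescribing.** A reader might also infer that a newness rule would cure any arm difference in antipsychotic prescribing. It would not: newly started drugs would still count, and a field for indication would be filled in by unblinded clinicians.

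**Conclusion.** The point holds for two secondary endpoints. As written, continued home antipsychotics score as delirium, and a balloon pump or assist device placed before surgery, or an assist device planned with another procedure, can score as prolonged low output state. The delirium case is the clearer one.

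The expected consequence is inflated rates in both arms and relative effects pulled towards 1, with little change in the risk difference. This assumes that randomisation balances the patients concerned. The size cannot be determined from the protocol: the shift of a risk ratio from 0.70 to between 0.72 and 0.78 is an illustration under assumed shares of 1 to 3% and true rates of 8 to 12%.

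The primary endpoint, its analysis and the sample size are untouched. This is a worthwhile tidying of definitions, not a threat to the trial.

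**What to change.** The changes concern outcome classification only, not the care of any patient.

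- **Delirium:** do not count the antipsychotic criterion for drugs already taken before surgery. Baseline medications are recorded (section 13.2 and the notes to the schedule in section 24.1), so home use can be identified.
- **Prolonged low output state:** count a balloon pump or assist device only if it was first placed after the start of surgery and was not planned beforehand. Device use is already collected among the surgical details (section 14.8); a field for timing of placement may be needed.
- **Acute kidney injury:** state in the separate renal analysis plan that patients on dialysis at baseline are not evaluable for this outcome.

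The qualifying phrases belong wherever the definitions are repeated: sections 4, 8.2, 15.2 and 19.5 for both outcomes, and also 14.12.1 for delirium. The cost is a few words in each place and at most one added field. The small downside is slightly weaker comparability with the predecessor trial, if that trial used the unqualified rules.

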#### 14.12.2 Clinical events at 6 month follow-up visit

At 6 months, an in-person follow-up visit (or telephone, if in-person is not possible) will occur to capture any new hospitalisations or emergency department visits, as well as the following clinical outcomes. A telephone script has been created to facilitate collection of this data, in case an in-person visit is not possible.

- All-cause mortality
- M
- New onset renal failure requiring dialysis
- Stroke
- Surgical or non-surgical coronary revascularisation
- COVID-19 test result (if done for clinical purposes)

The following will also be collected in the eCRF at the 6 month follow-up visit:

- Details for any **ECG(s) done for any incidence of MI** that occurs up to the 6 month visit, if applicable. Sites will be requested to send de-identified copy(ies) of the ECG(s) to the DCC.
- Details for the last ECG performed for clinical purposes. Sites will be requested to send a
  deidentified copy of the ECG for adjudication to the DCC via [contact].
- A **list of all medications** that the patient is taking at the 6 month follow-up visit.

Routinely collected healthcare data via Office for National Statistics (ONS) will be used to ascertain mortality at 6 months in UK participants. A telephone contact to participants who have not died (identified from NHS SPINE data) will occur at 6 months postoperatively to assess clinical outcomes. Laboratory parameters will be determined preoperatively, intraoperatively, daily for the first three days postoperatively then every second day until day 11 and thereafter as clinically indicated while in hospital, as in TRICS III.

Page **33** of **55** 

IRAS ID: 325425

#### 15. Evaluation of trial results

#### 15.1 Primary Endpoints

The primary outcome is primary composite endpoint of all-cause mortality, myocardial infarction defined in accordance with the 4th Universal Definition of Myocardial Infarction, new-onset renal failure with dialysis, or new focal neurological deficit (stroke) lasting more than 24 hours confirmed by clinical and/or computed tomographic scan, occurring within 6 months of the initial surgery.

#### 15.2 Secondary Endpoints

The secondary endpoints are as follows; see section 8.12 for definitions and details:

- 1. Incidence of each individual component of the primary outcome: all-cause mortality, myocardial infarction, new onset renal failure requiring dialysis, and new focal neurological deficit (stroke) within 6 months
- 2. Composite and individual all-cause mortality, myocardial infarction, new onset renal failure requiring dialysis, and new focal neurological deficit (stroke) with index hospitalisation or after 28 days postoperatively, whichever comes first Length of stay in the Intensive Care Unit (ICU) and hospital (index hospitalisation)
- 3. Prolonged low output state defined as the need for two or more inotropes for 24 hours or more, intra-aortic balloon pump or ventricular assist device postoperatively (index hospitalisation)
- 4. Duration of mechanical ventilation (index hospitalisation)
- 5. Infection: defined as septic shock with positive blood cultures; pneumonia defined as autopsy diagnosis or roentgenographic infiltrate and at least two out of three of the following criteria: fever, leukocytosis, and positive sputum culture; and/or deep sternal or leg wound infection requiring intravenous antibiotics and/or surgical debridement (index hospitalisation)
- 6. Acute kidney injury (AKI), defined by the Kidney Disease Improving Global Outcomes (KDIGO) clinical practice guideline46 a 50% increase in serum creatinine within 1 week or a 26.5 μmol/L increase within 48 hours (index hospitalisation)
- 7. Delirium, based on one of the following criteria: Confusion Assessment Method (CAM) or CAM-ICU (even on 1 occasion), or Intensive Care Delirium Screening Checklist (ICDSC) > 3, or 3D-CAM, or 4AT ≥4, or more than one dose of haloperidol or similar antipsychotic drug, or documented delirium by neurologist or neurosurgeon or psychiatrist consultation (index hospitalisation)
- 8. Gut infarction confirmed by imaging (e.g. angiography), autopsy, or through surgical means (index hospitalisation)
- 9. Hospital visits (hospitalisation and/or emergency visits and coronary revascularisation at 6 months)
- 10. The proportion of patients transfused and the number of blood products utilised (RBCs, plasma, platelets) (index hospitalisation)
- 11. Seizures, defined as generalised or focal tonic-clonic movements consistent with seizure; or electroencephalogram demonstrating epileptiform discharges; or diagnosis of seizures by neurologist or neurosurgeon consultation (index hospitalisation)
- 12. Encephalopathy, defined as unexpected delayed awakening or severely altered mental status (unconscious despite no sedative medication for more than 5 days), or encephalopathy documented by neurologist or neurosurgeon or psychiatrist consultation (index hospitalisation)

Page **34** of **55** 

IRAS ID: 325425

### 16. Statistical methods

Trial statistical analyses will be performed by researchers at the Li Ka Shing Knowledge Institute at the University of Toronto.

#### 16.1 Sample Size Estimation

TRICS IV is a superiority trial powered for the primary composite endpoint of all-cause mortality, myocardial infarction, new-onset renal failure with dialysis, or new focal neurological deficit (stroke), within 6 months after the initial surgery. A RR of 0.70, with an incidence rate for the primary endpoint of 14% in the liberal and 20% in the restrictive transfusion arm was used for the sample size calculation, which is in line with observed rates in the modified intention-to-treat (ITT) analysis of TRICS III in individuals younger than 69 years old. As observed in TRICS III, we assumed that 1.5% of the patients would be lost to follow-up by 6 months. With a 1:1 allocation ratio and a two-sided  $\alpha$ =0.05, we found that enrolment of a total of 1,440 patients (720 per group) would provide 85% power to detect a RR of 0.70 for the liberal as compared with the restrictive transfusion strategy while accounting for a 1.5% attrition rate and one interim analysis of the primary outcome. To ensure that the main analysis of the primary outcome has at least 80% power, we will conduct a conditional power analysis after 50% of the recruited participants have their primary outcome data available. If the conditional power is ≥60% but <80%, we will re-estimate the sample size needed so that the main analysis of the primary outcome has 80% power, and recruitment of participants will continue until the re-estimated sample size is reached. For all other values of conditional power, we will continue recruitment until the originally planned target sample size of 1,440 patients is reached.

We may include the first 100 randomised participants in an internal pilot assessment of the adherence to Hb triggers that utilize physiological changes for initiation of RBC transfusion.

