#### 16.2 Analysis population

The ITT population consists of all patients who underwent randomisation and subsequent cardiac surgery with available outcome data.

The per-protocol (PP) population consists of all participants who underwent randomisation and subsequent cardiac surgery with cardiopulmonary bypass with available outcome data, except for patients who had a protocol adherence of less than 90%, patients who were withdrawn from the trial by the treating physician at any time, and patients who withdrew consent.

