#### 16.4 Primary Outcome Analyses

The primary analysis of the primary outcome will be based on a chi-squared test. Superiority of liberal over restrictive transfusion will be declared with a p-value<0.05. A secondary analysis of the primary outcome will be based on a Cox regression model to derive hazard ratios (HR) with 95% confidence intervals, with the time to event presented per group using Kaplan Meier curves.

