#### 16.9 Missing Values

While we anticipate that the primary outcome will be available in >95% of patients, if the primary outcome is missing in more than 5% of patients, we will perform analyses to mitigate the effect of missing data as follows: we will develop a missing data model and perform a multiple imputation analysis. We will also carry out inverse-probability weighting. This is a two-stage model where a logistic regression model is first used to estimate the probability of not being missing. Then the analysis of the outcome proceeds on complete cases through a weighted analysis where the inverse probability of "completeness" forms the weights. The inference of the imputed model and inverseprobability weighting will be compared to that of the model with missing data.

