#### 18.1.2 Steps to minimise bias

- Randomisation and allocation concealment: The centralised, web-based randomisation system will ensure allocation concealment. In case of rare service interruptions that occur during non- business hours, each site will be provided with a back-up randomisation method. There were no such unanticipated service interruptions in TRICS III.
- Managing potential bias due to the unblinded nature of the trial: Blinding or masking of
  treatment allocation is not possible for the medical team administering transfusions.
  Knowledge of the Hb is essential for detecting early haemorrhage or for the use of blood
  conservation strategies as part of routine postoperative care. To address this key source of
  bias we aim to mitigate detection, procedural, and post randomisation bias using techniques
  that were effective in TRICS III and TITRE 2 such as
  - Masking clinical outcomes through a blinded adjudication
  - Masking the statistician and the DSMB when the data are presented for the interim

- Choosing objective outcomes with source data verification. Of the 3683 events that were adjudicated in TRICS III, only 156 (4%) required a third adjudicator. All discrepancies were easily resolved.
- Careful documentation of protocol non-adherence as per TRICS III including the application of pre-specified definitions of minor and major protocol deviations.
- Adherence and attrition: Patients have the right to discontinue from the trial or trial transfusion strategy for any reason, at any time. All participants who are randomised and undergo surgery will be followed for the remainder of the trial up to the 6-month outcome, unless the participant withdraws consent for follow up. Any participant who is randomised but for any reason does not undergo surgery, will not be followed and data will not be collected longitudinally. In this situation, the participant will be replaced to achieve the required sample size. Strategies to optimise adherence and reduce attrition developed in TRICS III and TITRE 2 will be applied. In both TRICS III and TITRE 2 severe non-adherence occurred in 9% of participants. Loss to follow-up for the primary outcomes of the TITRe2 trial and TRICS III trial were 4.8% at 90 days and 4.5 % at 180 days respectively.

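### Loss to follow-up in TRICS III is given as both 1.5% and 4.5%, and the 5% trigger means no missing-data analysis is required at any loss rate the protocol cites

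*Protocol*

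**What the plan says.** **Loss rate.** Section 16.1 states: "As observed in TRICS III, we assumed that 1.5% of the patients would be lost to follow-up by 6 months". It then says "we found that enrolment of a total of 1,440 patients (720 per group) would provide 85% power to detect a RR of 0.70", with that attrition and one interim analysis taken into account. Section 18.1.2 reports that losses for the primary outcome in the "TITRe2 trial and TRICS III trial were 4.8% at 90 days and 4.5 % at 180 days respectively". The scientific abstract (section 5) also plans on 4.5% attrition, there with 1,802 participants and 90% power.

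**Analysis set.** Section 16.2: "The ITT population consists of all patients who underwent randomisation and subsequent cardiac surgery with available outcome data".

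**Missing outcomes.** Section 16.9 expects the primary outcome in more than 95% of patients and continues: "if the primary outcome is missing in more than 5% of patients, we will perform analyses to mitigate the effect of missing data". The methods it names are multiple imputation and inverse-probability weighting, each to be compared with the unimputed result.

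**Tests.** Section 16.4 makes a chi-squared test the primary analysis and a Cox model with Kaplan-Meier curves a secondary analysis of the same outcome.

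**The concern.** Two sections attribute loss rates that differ threefold to the same earlier trial at the same time point, and the sample size rests on the lower one. As written, at least one statement is wrong or the two count different things without saying so.

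The second problem comes from sections 16.2 and 16.9 read together. A patient without an outcome is outside the ITT set by definition, so the patients whom section 16.9 would impute do not belong to the population being analysed. The trigger also sits above every loss rate the protocol mentions, so in the situation the protocol expects, nothing beyond the observed outcomes need be examined.

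Allocation is open-label (section 10.4) and participants may withdraw consent to follow-up (section 10.6), so loss could differ between arms. The share of outcomes missing does not show whether the missingness is informative. If the primary result were close, the plan would offer no agreed analysis of what the missing outcomes could do to it.

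**Working it through.** **Inputs.** Event rates 20% restrictive and 14% liberal, two-sided alpha 0.05, 1:1 allocation, 720 per arm (section 16.1). Interim at 50% with Z = 2.75, final Z = 1.98 (section 16.6). Loss d = 1.5% (section 16.1) or 4.5% (section 18.1.2 and abstract).

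**1. The stated 85% reproduces.** Evaluable patients per arm: n = 720 × (1 − 0.015) = 709.2.
- Pooled SE: √(2 × 0.17 × 0.83 / 709.2) = 0.01995.
- Unpooled SE: √((0.20 × 0.80 + 0.14 × 0.86) / 709.2) = 0.01988.
- Fixed-sample power: Φ((0.06 − 1.96 × 0.01995) / 0.01988) = Φ(1.051) = 85.3%.
- With the two boundaries (bivariate normal, correlation √0.5): 85.0% to 85.2%, depending on which SE is used.

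**2. At 4.5% loss.** n = 720 × (1 − 0.045) = 687.6 per arm. The SEs become 0.02026 and 0.02019.
- Fixed-sample power: Φ((0.06 − 1.96 × 0.02026) / 0.02019) = Φ(1.005) = 84.3%.
- With the boundaries: 83.9% to 84.1%.

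The fall is about 1 percentage point. Holding 85% at 4.5% loss would need 1,474 patients (fixed sample) or 1,480 (group sequential).

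**3. The trigger against the cited loss rates.**

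| Loss rate | Where cited | Above 5%? | Section 16.9 analyses required? |
|---|---|---|---|
| 1.5% | 16.1 (TRICS III, 6 months) | No | No |
| 4.5% | 18.1.2 (TRICS III, 180 days); abstract | No | No |
| 4.8% | 18.1.2 (TITRe2, 90 days) | No | No |

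**4. How much the missing outcomes could move the result.** At 4.5% loss, 0.045 × 1,440 = 64.8 patients are unobserved, about 32 per arm. The planned result on 688 per arm is 0.14 × 688 ≈ 96 liberal and 0.20 × 688 ≈ 138 restrictive events, with pooled Z = 3.01.

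Now add 32 patients back to each arm, give both arms the same 5 background events (about 17% of 32), and add x further events to the liberal arm:
- x = 13: 114 v 143 on 720 per arm, Z = 2.00, still above 1.98.
- x = 14: 115 v 143 on 720 per arm, Z = 1.92, significance lost.

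About 14 excess events among 32 patients is a difference in risk of 14/32 ≈ 44 percentage points among the missing.

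Near the boundary the picture changes. With 138 restrictive events on 688 per arm, the smallest significant gap is 29 (109 v 138, Z = 2.04); a gap of 28 gives 1.96. Adding back 32 per arm with 5 background events each gives Z = 2.00, and one further liberal event gives 1.92.

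**The case against.** Several points on the other side stand.

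- **Power.** A reader might infer that the 85% is a miscalculation or that the trial is underpowered. Neither follows. The 85% is correct for its 1.5% input, the loss of about 1 point leaves power above the 80% floor, and section 16.1 provides for sample-size re-estimation. The protocol also states totals of 1,760 and 1,802, which at 4.5% loss give about 90.6% and 91.3% (fixed sample); that discrepancy is a separate matter.
- **Complete cases only.** A reader might infer that nothing in the plan uses partial follow-up. Section 10.6 retains data collected up to discontinuation, and the secondary Cox model can censor. This protection is only partial: censoring assumes non-informative loss, and the section 16.2 wording may keep these patients out of the Cox model too.
- **Selective retention.** It is tempting to say that patients with an event before loss are kept while event-free patients are dropped. Section 16.2 does not define an available outcome for the composite, so this is inference.
- **Size.** Setting about 65 missing patients against the planned difference of 42 events (138 − 96) mixes units. At 17% average risk, 65 patients would have about 11 events.
- **Differential loss.** It is possible but not shown. Patients who stop the transfusion strategy stay in follow-up unless they withdraw consent. In the UK, linked records recover deaths, though not MI, stroke or dialysis, and not outside the UK.
- **SAP territory.** Imputation details and tipping-point methods can be left to the SAP. The 5% trigger and the ITT definition are fixed in the protocol itself, so this answer does not cover them.

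**Conclusion.** The point holds in two parts.

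First, the loss rates in sections 16.1 and 18.1.2 contradict each other as written. The documents cannot settle which is right: the source is not at hand, and the figures may count different things, such as lost contact and missing primary outcome. If 4.5% applies, power at 1,440 is about 84%, a minor correction.

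Second, sections 16.2 and 16.9 together make the primary test complete-case under an ITT label, with no required missing-data sensitivity analysis at any loss rate the protocol cites. This carries the greater weight. It does not show that the result would be biased. At the planned effect the conclusion is robust, since about 14 excess liberal events among some 32 missing per arm would be needed to overturn it. Near the boundary, one or two would do.

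These figures assume the planned event rates, 4.5% loss split equally between arms, equal background events among the missing, and the final boundary of 1.98.

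**What to change.** 1. In sections 16.1 and 18.1.2 and the abstract, use one sourced loss rate, or state what each figure counts. If 4.5% applies, restate power at 1,440 as about 84%.
2. In section 16.2, define ITT as every randomised patient who had surgery, analysed in the allocated arm, whether or not the outcome is available.
3. In section 16.9, delete the 5% trigger, so that the multiple imputation and inverse-probability weighting already named there are run as sensitivity analyses whatever share is missing. A tipping-point analysis is optional and can be specified in the SAP.

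The cost is wording and a small amount of analysis. The stated power may fall by about 1 point, and no extra patients are needed.
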